5. STUDY'S AIM AND OBJECTIVES

AIM: To obtain pilot data to test the hypothesis that aeroallergen sensitisation (confirmed by a wheal formation with a diameter ≥ 3 mm after a skin prick test is performed), FeNO (offline method) ≥ 10 ppb and a peripheral blood eosinophil count $\geq 300/\mu\text{l}$, alone or in combination, can predict future wheezing exacerbations in preschool children as well as response to treatment with inhaled corticosteroids, as a preliminary to a large, randomised controlled trial. Also, that these tests are acceptable to families.

OBJECTIVES:

- To recruit 100 preschool children with a history of wheeze, aged one to five years old, and determine atopic status, peripheral blood eosinophil count (point of care test) and FeNO (offline method).
- To evaluate the feasibility and acceptability of these tests
- To categorize the children according to the biomarkers tested and assess whether any or all, alone or in combination, predict future wheezing exacerbations as well as determine the clinical outcome over one year
- To obtain parents' and doctors' insights into whether the biomarkers mentioned above could be used in a future intervention study.

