6.1. STUDY OUTCOME MEASURES

Primary outcome:

Acute attacks of wheeze defined as requiring an unscheduled health care visit

Secondary outcomes:

- Carer days off work
- Days the child unable to attend childcare facility
- Use of oral corticosteroids
- Use of inhaled β -2 agonist (rescue therapy)
- Assessment if children's respiratory or wheezing condition is under control by using the TRACK™ score questionnaire (Test for Respiratory and Asthma Control in Kids) (Appendix 3).

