9. ASSESSMENT AND FOLLOW-UP

We will arrange for a short monthly electronic questionnaire to be sent by email to the parents/carers, in order to record on a monthly basis, the days their child was out of childcare, days the carer missed from work, unscheduled health care visits and use of rescue therapy or oral corticosteroids (including dosage) (Appendix 4: Monthly Questionnaire). In addition, we will record the children's TRACK™ score (Test for Respiratory and Asthma Control in Kids) (Appendix 3: TRACK™ score questionnaire) every 3 months, to assess wheeze control. There will be review visits every 3 months, to evaluate their progression in person, but if not feasible, video calls will be arranged through Microsoft Teams. In the case of any incidental findings, there will be thorough evaluation of potential benefits or harms before disclosing the information to the child's parent. As this is an observational study, no interventions can be done in the case of incidental findings and parents will be advised to discuss this with their child's GP or paediatrician.

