10. END OF STUDY

The end of the study will be when the last of the 100 participants completes his follow-up period of 12 months with his/her last study visit. The anticipated finishing date is December 2023.

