13.5. DIRECT ACCESS TO SOURCE DATA

The Investigator(s)/institution will permit study-related monitoring, audits, REC review, and regulatory inspection(s), providing direct access to source data/documents. Parents will be informed of this during the informed consent discussion. Parents will be asked to consent to provide access to their medical notes.

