19.4. APPENDIX 4: MONTHLY QUESTIONNAIRE

Introduction: Please take a moment to complete the following questionnaire relating to your child's wheezing condition. The questions will help us identify wheezing exacerbations and assess your child's quality of life.

Question 1: Did your child experience any wheezing symptoms during the last month?

Not at all	Once or twice	Once every week	2 or 3 times a week	4 or more times a week
				

Question 2: Was the child unable to go to childcare because of breathing problems?

Yes	No	N/A
		

If **yes**, please state how many days: _____ (Number)

Question 3: Did you have to take your child for an emergency appointment with your GP, urgent care or hospital because of wheezing?

Not at all	Once or twice	Once every week	2 or 3 times a week	4 or more times a week
				

Question 4: Was your child treated with inhaled or oral corticosteroids?

Yes	No
	

If **yes**, what was the dose, frequency and duration?

Dose:	Frequency:	Duration:
_____	_____	_____

Question 5: Was your child given β 2 agonists (blue inhaler, rescue therapy)?

Yes	No
	

If **yes**, what was the dose, frequency and duration?

Dose:	Frequency:	Duration:
_____	_____	_____

Question 6: Did you have to take days off work because your child had wheezing or breathing difficulties?

Yes	No
	

If **yes**, how many days did you take? Specify number: _____ (days)

Survey's ending message: "We thank you for your time spent taking this survey. Your response has been recorded."

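### The form item that supplies the primary outcome asks about emergency appointments, while the outcome is any unscheduled visit, so some qualifying visits may go unrecorded

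*Combined protocol and SAP*

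**What the plan says.** Section 6.1, like the Study Summary in section 2, gives the primary outcome as "Acute attacks of wheeze defined as requiring an unscheduled health care visit". Unscheduled is not defined further.

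Section 9 says what the monthly form is meant to collect, including "unscheduled health care visits and use of rescue therapy or oral corticosteroids (including dosage) (Appendix 4: Monthly Questionnaire". The Study Summary, sections 6 and 7.1 and Appendix 2 say the same.

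In Appendix 4, Question 3 is the only item about visits. It reads "Did you have to take your child for an emergency appointment with your GP, urgent care or hospital because of wheezing". The answers run from *Not at all* through *Once or twice* to *4 or more times a week*. Emergency is not defined either. The other items cover symptoms (Question 1), childcare absence (2), corticosteroids (4), reliever use (5) and the carer's lost work (6).

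Two other contacts with the data are mentioned. Section 9 states: "There will be review visits every 3 months, to evaluate their progression in person". Section 13.5, on monitoring and audit, states: "Parents will be asked to consent to provide access to their medical notes". Neither is named as a source or check for the primary outcome.

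**The concern.** The outcome and the question that measures it are not the same set of events. The outcome turns on whether the visit was planned. The question turns on whether it was an emergency, and on whether the parent had to take the child somewhere. A visit can be unplanned without being an emergency in the family's eyes. Such a visit meets section 6.1 and fails Question 3.

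Two things are at stake. Section 4.3 says the study should supply pilot data for the power calculation of a later trial, so a rate collected on a narrower definition than the stated one would be carried forward under the wrong label. And if milder attacks are less often called emergencies, capture would depend on severity. Should severity also differ by biomarker status, the comparison the study was set up to make would be affected. Sections 4.1 and 4.3 place most of these children in primary care, where a same-day appointment is an ordinary route to being seen.

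**Working it through.** The plan gives no power, effect size, attack rate or justification for its sample size, so there is no figure to reproduce. The documents supply 100 children (section 5: "To recruit 100 preschool children with a history of wheeze, aged one to five years old"), 12 months of follow-up each (section 10) and a 0.05 significance level (section 11). Every other number below is assumed.

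**1. Outcome against question.**
- Same-day GP or nurse visit, unplanned, not thought an emergency: inside section 6.1; *Not at all* is a truthful answer to Question 3.
- Walk-in visit of the same kind: same result.
- Unplanned attendance at home: inside section 6.1; the parent did not take the child to an appointment.
- Ambulance attendance ending in hospital: inside section 6.1, and would probably be reported under hospital.
- Telephone or video consultation: not clearly a visit, so not clearly inside section 6.1.

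The gap is therefore mainly the first three. No other Appendix 4 item asks about visits.

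**2. Effect on the count of visits.** If a share m of qualifying visits is not reported, recorded rate = true rate × (1 − m). For a true rate of 1.0 per year and m = 10%, 20% or 30%, the recorded rate is 0.9, 0.8 or 0.7.

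**3. Effect on the count of attacks.** The answer bands intervene. Suppose each month with a visit truly had one visit, and 20% are missed. The recorded total relative to the truth depends on how *Once or twice* is coded:
- coded 1: 0.8 × 1 = 0.8
- coded 1.5: 0.8 × 1.5 = 1.2
- coded 2: 0.8 × 2 = 1.6

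The question also counts visits rather than attacks, so two visits for one attack would add to the total. The sign of the net error is not fixed.

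**4. Power, equal loss in both groups (illustration).** Assume 40 marker-positive and 60 marker-negative children, with risk of any attack 60% and 35%. Power = Φ[(|p1 − p2| − 1.96·se0)/se1], with se0 from the pooled proportion and se1 from the separate ones. With a share m of children with an attack recorded as having none:
- m = 0: 0.697
- m = 10% (54% against 31.5%): 0.614
- m = 20% (48% against 28%): 0.532
- m = 30% (42% against 24.5%): 0.455

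The risk ratio stays at 0.60/0.35 = 1.71 throughout.

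**5. Power on counts (illustration).** Assume the same 40/60 split, negative-binomial counts with shape 1, 1.5 attacks per year in marker-negative children, a true rate ratio of 2 and a Mann-Whitney test. Repeated simulations gave power of 66–67% at full capture, 63–66% at 80%, 59–60% at 60% and 55–58% at 50%.

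**6. Unequal loss (illustration).** With no true difference, capture of 80% in marker-positive and 60% in marker-negative children gives an apparent rate ratio of 0.80/0.60 = 1.33. The simulated false-positive rate is 15–16%. With 80% against 70% it is about 7%.

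**7. Later trial (illustration).** For a 30% reduction, 80% power and shape k = 1, n per arm = (1.96 + 0.8416)² × (1/μ + 1/(0.7μ) + 2/k) / (ln 0.7)², where the constant is 7.849/0.1272 = 61.7.
- μ = 1.5 (full capture): 61.7 × 3.619 = 223
- μ = 1.2 (80%): 61.7 × 4.024 = 248
- μ = 0.9 (60%): 61.7 × 4.698 = 290
- μ = 0.75 (50%): 61.7 × 5.238 = 323

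**The case against.** Question 3 is not confined to the emergency department. It names the GP first, then urgent care and hospital, which are the main settings for these visits. Five places in the protocol describe Appendix 4 as recording unscheduled visits, so the intent is clear, and many parents may read an emergency GP appointment as any same-day unplanned one. The quarterly reviews and the notes could bring missed visits to light, and the case report form, which is not part of the documents, may ask about them. This is also a 100-child feasibility study, and no stated figure would change.

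Much of that stands. A reader might infer that visits *are* missed and that the attack rate *is* under-counted. The documents contain no reporting data to show it, and step 3 shows that the net error in attacks can run either way. A reader might also list telephone and video consultations among the losses, but the outcome is a visit and they are not clearly within it.

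What does not stand is the view that naming the settings cures the problem. The list says where the appointment took place; emergency still says what kind it was. Nor are the reviews or the notes specified as a check. Better answer bands would not help either: a visit answered *Not at all* is lost under any coding.

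**Conclusion.** The mismatch is certain, because it can be read from sections 6.1 and 9 and Appendix 4. Its consequence is a possibility: some unplanned same-day, walk-in or home visits may go unrecorded, and capture could differ with attack severity. The documents do not allow the size, or the net direction of error in the attack count, to be computed.

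The figures for power, false positives and later trial size show what would follow under assumed rates, group sizes and capture shares. They are not estimates for this study. With counts and 80% capture, power hardly moves. The 15–16% false-positive rate needs an assumed 20-point gap in capture. A reader might infer that the pilot rate passed to the later trial is too low, or that a biomarker will look falsely predictive. Neither is supported: the first needs the answer bands and repeat visits not to offset the loss, and the second needs severity and reporting to differ by biomarker status, on which the documents give no data.

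This is more than missing detail, since following the form as written can lose events that the protocol defines as outcomes. It merits correction because the remedy is small.

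**What to change.** Reword Question 3 to the section 6.1 definition, for example: *Because of wheezing, did your child have any visit that was not planned in advance (GP or nurse, walk-in or urgent care, out-of-hours, home or ambulance attendance, emergency department, hospital)?* Give one tick box per type.

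Count all unscheduled visits for the primary outcome. Record telephone or video contacts separately and outside it. Report emergency-only visits as a sensitivity analysis, stating beforehand which boxes make up that subset.

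The cost is a slightly longer item in one electronic questionnaire and an ethics notification. If children are already enrolled, the change of wording must be noted in the analysis, with a record of which wording each monthly return used. Clinical care is unaffected. The answer bands are a separate weakness of the same item, and could be revised when it is reissued.

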6. STUDY DESIGN

This is a pragmatic, observational study involving preschool children with wheeze aged one to five years old. All treatment and routine monitoring decisions will be at the discretion of their treating general practitioner (GP) or paediatrician (as per usual clinical practice), blinded to the study measurements. After clinical consultation and following submission of the electronic informed consent through the Qualtrics® platform (offered by Imperial College London), the parent/carer will be asked to give the contact details of the child's GP or paediatrician, who will be informed about child's participation in this study through a letter sent to his/her email along with the patient information sheet. The parent carer will be then shown a standard video questionnaire and will be asked to identify what respiratory sounds their children have been making. The child will be booked for the three biomarker tests [atopic sensitisation, blood eosinophil count and FeNO (off-line method)]. The tests will be carried out once and at a time of clinical stability. In this visit, a sample of the child's exhaled tidal breath will be collected in a suitable bag in duplicate for offline measurement of FeNO later on with chemiluminescence. Skin prick tests will be performed to: (a) house dust mite, (b) grass pollen, (c) tree pollen, (d) cat hair(e) dog hair, as well as normal saline and histamine and these will be applied on either the child's back, leg or arm. If the child has been prescribed antihistamines, we will ask for these to be withheld for 72 hours prior to skin prick testing. FeNO values (offline method) ≥ 10 ppb will indicate Type 2 inflammation and wheal diameter, measured with a specialised skin prick test ruler, ≥ 3 mm will indicate sensitisation to the applied aeroallergen. In addition, skin prick tests will allow the assessment of which aeroallergen is the most useful predictor of outcomes in preschool children. Finally, the peripheral blood eosinophil count will be measured from a finger prick blood sample, using the Haemocue machine, allowing a result in approximately 2 minutes. Values ≥ 300 cells/ μ l indicate Type 2 inflammation. All tests will normally take no more than one hour.

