Follow-up: We will arrange for a short monthly electronic questionnaire to be sent by email to the parents/carers, in order to record on a monthly basis, the days their child was out of childcare, days the carer missed from work, unscheduled health care visits and use of rescue therapy or oral corticosteroids (including dosage) (Appendix 4: Monthly Questionnaire). In addition, we will record the children's TRACK™ score (Test for Respiratory and Asthma Control in Kids) (Appendix 3: TRACK™ score questionnaire) every 3 months, to assess wheeze control. The questionnaires will be made and sent through the Qualtrics® questionnaire platform (offered by Imperial College London). There will be review visits every 3 months, to evaluate their progression in person, but if not feasible, video calls will be arranged through Microsoft Teams. Correct use of spacers will be ensured after guiding parents on how to use them and will be done by their GP or paediatrician as well as from [name] who is a registered pharmacist in the UK.

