7.2. INCLUSION AND EXCLUSION CRITERIA

7.2.1. CHILDREN

INCLUSION CRITERIA	EXCLUSION CRITERIA

1. Patients aged one to five years old presenting to primary care or to the emergency department or to secondary care (e.g., outpatients) or identified from primary care records and have been diagnosed with wheezing by their GP or paediatrician who has decided to prescribe any bronchodilator, ICS or montelukast on clinical grounds
	
1. Inability to understand and cooperate with study procedures
 
2. Significant co-morbidity (respiratory or otherwise), for example cystic fibrosis (excluding atopic disorders such as eczema, allergic rhinitis and food allergy)
 
3. Withholding or withdrawal of informed consent

2. Parents/Carers able to understand and familiarize themselves with the study and are willing to provide informed consent
	
4. Severe procedural anxiety (needle phobia)
 
5. Child is already enrolled in another study involving investigational medicinal product (CTIMP)
 
6. History of near-fatal asthma that resulted in intubation / assisted ventilation.

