19.2. APPENDIX 2: FOLLOW-UP PLAN

We will arrange for a short monthly electronic questionnaire to be sent by email to the parents/carers, in order to record on a monthly basis, the days their child was out of childcare, days the carer missed from work, unscheduled health care visits and use of rescue therapy or oral corticosteroids (including dosage) (Appendix 4: Monthly Questionnaire). In addition, we will record the children's TRACK™ score (Test for Respiratory and Asthma Control in Kids) (Appendix 3: TRACK™ score questionnaire) every 3 months, to assess wheeze control. The questionnaires will be made and sent through the Qualtrics® questionnaire platform (offered by Imperial College London), which allows data gathering data according to the GCP guidelines and as used for years in the Breathing Together study (19). Additionally, the questionnaire form submission will not collect parents' IP address or geolocation. There will also be review visits every 3 months, to evaluate their progression in person, but if not feasible, video calls will be arranged through Microsoft Teams.

	Months											
	1	2	3	4	5	6	7	8	9	10	11	12
Primary Care Visit		X			X			X				X
Video Call (Microsoft Teams) ¹		X			X			X				X
Biomarker Testing ²			X ³									
TRACK™ Score Questionnaire ⁴			X			X			X			X
Monthly Questionnaire	X	X	X	X	X	X	X	X	X	X	X	X
Focus Group												X

Table 2. The follow-up plan after preschool wheezers' recruitment.

¹ In case they are not available for primary care visit

² Testing the 3 biomarkers, blood eosinophils, atopic sensitisation and FeNO (offline method).

³ A second testing will be performed 3 months after the first one and will be **optional**. Parents will be informed through the patient information sheet, as well as in person that they have the option to deny participation of their child in this second testing. It is written in the informed consent form as well.

⁴ The TRACK™ score will be sent to the parents/carers by email or SMS every 3 months and will be incorporated to the monthly questionnaire. They will be sent through the Qualtrics® questionnaire platform.

19.3. APPENDIX 3: TRACK™ SCORE QUESTIONNAIRE (TEST FOR RESPIRATORY AND ASTHMA CONTROL IN KIDS)

1. During the past 4 weeks, how often was your child bothered by breathing problems, such as wheezing, coughing or shortness of breath?
					
Not at all	Once or twice	Once every week	2 or 3 times a week	4 or more times a week	

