 20	 15	 10	 5	 0	

2. During the past 4 weeks, how often did your child's breathing problems (wheezing, coughing, shortness of breath) wake him or her up at night?
					
Not at all	Once or twice	Once every week	2 or 3 times a week	4 or more times a week	
 20	 15	 10	 5	 0	

3. During the past 4 weeks, to what extend did your child's breathing problems, such as wheezing, coughing or shortness of breath, interfere with his or her ability to play, go to school or engage in usual activities that a child should be doing at his or her age?
					
Not at all	Slightly	Moderately	Quite a lot	Extremely	
 20	 15	 10	 5	 0	

4. During the past 3 months, how often did your need to treat your child's breathing problems (wheezing, coughing or shortness of breath) with quick relief medications (e.g., albuterol, Ventolin®)
					
Not at all	Once or twice	Once every week	2 or 3 times a week	4 or more times a week	
 20	 15	 10	 5	 0	

5. During the past 12 months, how often did you child need to take oral corticosteroids (e.g., prednisone, prednisolone, Decadron®)
					
Not at all	Slightly	Moderately	Quite a lot	Extremely	
 20	 15	 10	 5	 0	

Total Score

Figure 1. The TRACK™ Score Questionnaire. TRACK (Test for Respiratory and Asthma Control in Kids) is a trademark of AstraZeneca group of companies © 2009. TRACK score less than 80 means that the child's breathing problems are out of control. TRACK score above 80 means that the child's breathing problems seem to be in control.

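### Question 4 of the monthly form pools inhaled and oral corticosteroids, so for a child on ICS a Yes does not show whether an oral course was given or which drug the dose refers to

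*Combined protocol and SAP*

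**What the plan says.** - Section 6.1 lists "Use of oral corticosteroids" as a secondary outcome, as does the Study Summary (Section 2).
- Section 6 says parents report each month "use of rescue therapy or oral corticosteroids (including dosage) (Appendix 4: Monthly Questionnaire"). Section 9 repeats "use of rescue therapy or oral corticosteroids (including dosage"). Sections 2 and 7.1 and Appendix 2 say the same. All of them point to Appendix 4 as the form.
- Appendix 4 asks "Question 4: Was your child treated with inhaled or oral corticosteroids". The answer is Yes or No. After a Yes there is one line with blanks for dose, frequency and duration.
- Section 7.2.1 admits children diagnosed by a GP or paediatrician "who has decided to prescribe any bronchodilator, ICS or montelukast on clinical grounds".
- TRACK item 5 (Appendix 3) asks "During the past 12 months, how often did you child need to take oral corticosteroids". Footnote 4 to Table 2 in Appendix 2 says TRACK is sent "every 3 months and will be incorporated to the monthly questionnaire".
- Section 11 lists significance tests. It does not say how oral corticosteroid use is derived.

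**The concern.** The form named as the source asks a wider question than the outcome it is meant to supply. A child on regular ICS correctly answers Yes every month, with or without an oral course, so that child's tick says nothing about oral use. A child who had both drugs has one line for two regimens.

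The study is meant to compare outcomes between biomarker groups and to supply pilot data for the power calculations of a larger trial (Section 4.3). An oral-steroid outcome built on answers that cannot be separated by route would serve neither purpose well.

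**Working it through.** The plan states no figure to reproduce. The check is first a reading of the form against its stated purpose, then an illustration under assumed rates.

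**Step 1. What a correct answer to Question 4 reveals.**

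| Steroid that month | Tick | Dose line |
|---|---|---|
| None | No | blank |
| Inhaled only | Yes | inhaled regimen |
| Oral only | Yes | oral regimen |
| Both | Yes | one line for two regimens |

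Three of the four states give the same tick. Only a No settles oral use. After a Yes, the route depends on what the parent happens to write, because neither drug nor route is requested.

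**Step 2. What TRACK item 5 adds.** Table 2 schedules 12 monthly questionnaires, with TRACK at months 3, 6, 9 and 12. So 12 of 12 forms carry Question 4, 4 of 12 also carry the oral-only item, and 12 − 4 = 8 do not. For 100 children with every form returned (an upper limit), that is 100 × 12 = 1,200 answers to Question 4 and 100 × 4 = 400 to item 5.

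Item 5 looks back 12 months, so at month m its window starts 12 − m months before enrolment: 9, 6, 3 and 0 months at m = 3, 6, 9 and 12. Only the month-12 answer matches the follow-up year, as any/none. Read in sequence, the answers can give coarse timing: Not at all at month 3, then a positive answer at month 6, places a course in months 4 to 6. A child whose first answer is positive gives no such timing until a later Not at all. The item never gives a dose.

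**Step 3. Illustration: the bare tick box as the outcome.** No section proposes this, and the documents give no rates. Let p be the share of child-months on ICS and q the share with oral steroids. Both are assumed, and taken as independent.

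P(Yes) = p + (1 − p)q

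*Equal p in both groups.* The observed difference is (1 − p)(q1 − q0).

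| p | Share of true difference kept | Ratio seen when truth is 15% vs 5% (3.0) |
|---|---|---|
| 0.3 | 70% | 0.405 / 0.335 = 1.21 |
| 0.5 | 50% | 0.575 / 0.525 = 1.10 |
| 0.7 | 30% | 0.745 / 0.715 = 1.04 |

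This is bias toward no difference, and it needs no imbalance in ICS use.

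*Equal q, p = 0.5 against 0.4.* The observed difference is 0.1(1 − q): 0.097 at q = 0.03 and 0.090 at q = 0.10. A gap of 9.0 to 9.7 percentage points appears where there is none.

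*Share of Yes answers that reflect oral use*, q / P(Yes): from 0.05 / 0.715 = 0.07 (p = 0.7, q = 0.05) to 0.15 / 0.405 = 0.37 (p = 0.3, q = 0.15).

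**The case against.** The best defence is that the team has other ways to tell the drugs apart. The blanks are open text, and nothing stops a parent from naming the drug or writing two regimens; where only one steroid was given, the dose units and duration may identify it. Sections 6 and 7.1 record why ICS was stopped and count additional prescribed medication as treatment failure, so some treatment changes are tracked. Oral steroid status must be known before biomarker testing, which is delayed after a prescription. There are three-monthly reviews, a CRF, and consent to access medical notes (Section 13.5). All of this stands as a means of classifying some months. But no section makes any of it the source for this outcome, and no coding rule is given. I have not seen the CRF or all of Appendix 1 and make no claim about what they record.

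It is also fair that this is one secondary outcome in a feasibility study, and that Step 3 measures an endpoint nobody has proposed. Both points limit the weight of the finding. They do not remove the mismatch between the form and its stated purpose.

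Two stronger readings are tempting and not supported. A reader might infer that pooling is why the number of oral courses is unavailable. Question 4 has no count field for any child, and the plan promises use and dosage, not a count. A reader might also infer that ICS use differs by biomarker group and so creates a false difference. Treatment is left to the GP or "paediatrician (as per usual clinical practice), blinded to the study measurements". Families do learn the skin prick results (Section 5.1), so a difference is possible for that marker, but no section shows one.

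**Conclusion.** The point holds. For children taking ICS, month-level oral corticosteroid use and its dose cannot be reliably separated from inhaled use on the form that the protocol names as the source. This rests on the wording alone and needs no assumed rate. It affects every monthly form on which such a child's parent answers Yes; how many that is cannot be said, because the share of children on ICS is not given.

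The effect on a between-group comparison is of unknown size. The figures in Step 3 depend on assumed rates, on independence of inhaled and oral use, and on use of the tick box as the endpoint.

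It would go too far to conclude that the outcome is lost: No answers, informative free text and the yearly any/none answer from TRACK item 5 remain. Nor is the primary outcome touched, since unscheduled visits are asked about separately in Question 3. The change is worth making because it is cheap and lets the study report an outcome it has stated.

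**What to change.** 1. **Form.** Split Question 4 into an oral item and an inhaled item, each with Yes/No, product, dose, frequency and duration. A count of oral courses is an optional addition.
2. **Section 11.** State that oral corticosteroid use is derived from the oral item, with medical notes or the review visit as the month-level back-up. The month-12 TRACK item 5 can back up only the yearly any/none outcome, except that Not at all there rules out an oral course in every follow-up month.
3. **Forms already returned.** Classify them without sight of biomarker results. No means no oral course. A Yes is classified from the free text (drug, route, or a pre-stated rule on dose units and duration), then from the back-up source, and is otherwise unclassifiable.
4. **Reporting.** Give the unclassifiable share by biomarker group. Run the comparison twice, with those months counted once as no oral course and once as an oral course.

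**Cost.** Question 4 grows from 4 fields to 2 × 5 = 10, so at most 6 more a month; a family answering No to both ticks one extra box. The form needs an amendment with sponsor and HRA review. If collection has begun (the planned start was 01.09.2021), the data will differ before and after the change, and returned Yes forms must be classified by hand.

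### Appendix 4, Question 5 asks how much rescue inhaler was used but gives no countable unit; a days-of-use field would make this secondary outcome analysable (cheap improvement)

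*Combined protocol and SAP*

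**What the plan says.** Section 6.1 lists the outcome as "Use of inhaled β -2 agonist (rescue therapy"). It gives no unit, summary measure or derivation. Section 11 names the t-test or Mann-Whitney test for two-group comparisons of quantitative variables and chi-squared or Fisher's test for categorical ones, but assigns none of them to this outcome.

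Section 6 commits the monthly questionnaire to recording "use of rescue therapy or oral corticosteroids (including dosage"), and Appendix 2 repeats this. Table 2 in Appendix 2 schedules the form in each of 12 months.

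In Appendix 4, Question 5 is a Yes/No item about β2 "agonists (blue inhaler, rescue therapy"). A Yes leads to "what was the dose, frequency and duration", with one blank for each. On the same form, Question 2 (childcare absence) and Question 6 (days off work) each ask for a number of days.

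The TRACK questionnaire (Appendix 3, item 4) asks how often over the past 3 months breathing problems were treated "with quick relief medications (e.g., albuterol, Ventolin"). It has five ordered answers and is sent at months 3, 6, 9 and 12.

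**The concern.** The plan intends to collect the amount of reliever use, but Question 5 does not produce a number. Frequency could mean times per day, per week or per month. Duration could mean the length of one episode or the total over the month. There is no second line for a second episode, and as-needed use on scattered days has no natural duration. No rule says how the three blanks become a variable.

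Two things are at stake. First, the comparison between biomarker groups may in practice fall back on counting Yes-months, which carries less information than days of use. Second, section 4.3 says pilot data are needed to inform power calculations for a later trial. If rescue use is to be an outcome there, planning needs the mean and spread of an amount. Yes-months do not supply these, and uncoded free text does not supply them reliably.

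**Working it through.** **1. The plan's own figure.** There is none to reproduce. The documents state no power, effect size, rate of reliever use or marker-positive share. The 100 children are a recruitment target (section 5).

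**2. The items side by side.**

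| Item | Period | Answer | Can it be summed over the year? |
|---|---|---|---|
| Question 2, childcare | monthly | Yes/No/N/A, then number of days | Yes |
| Question 6, work | monthly | Yes/No, then number of days | Yes |
| Question 5, reliever | monthly | Yes/No, then three blanks without units | Only if each entry can be interpreted |
| TRACK item 4 | 3-monthly | five ordered bands, top band 4 or more times a week | No; four coarse readings a year |

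Question 5 is the monthly item tied to the listed reliever outcome, and it lacks the numeric field used in Questions 2 and 6.

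**3. What scoring could cost, on assumptions.** From the documents: 100 children, 12 reports each, significance level 0.05 (taken as two-sided). Everything else is assumed. Days of use for child i in month j are Poisson with mean μ × RR (marker-positive children only) × f(i) × h(i,j), capped at 30. Here f is a child-level gamma with mean 1 and variance 1, and h is a month-level gamma with mean 1 and variance 1 or 4. Assumed values: μ = 1, 3 or 6 days a month; RR = 1.5 or 2.0; marker-positive share 30% or 50%; all 12 forms returned. This gives 3 × 2 × 2 × 2 = 24 scenarios with 800 runs each, so the standard error of one power value is at most √(0.25/800) = 1.8 points.

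Three yearly scores were compared by Mann-Whitney test:
- A: exact total days.
- B: total days from free text, every entry codable, with multiplicative recall error (log-SD 0.5).
- C: number of Yes-months (0 to 12).

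| Share, μ, RR, month variance | A | B | C | A − B | A − C |
|---|---|---|---|---|---|
| 30%, 1, 1.5, 1 | 30.2% | 30.2% | 27.0% | 0.0 | 3.2 |
| 50%, 1, 1.5, 1 | 38.2% | 37.0% | 35.4% | 1.2 | 2.8 |
| 50%, 3, 2.0, 1 | 78.2% | 77.8% | 62.4% | 0.4 | 15.8 |
| 30%, 6, 2.0, 4 | 56.5% | 51.1% | 36.8% | 5.4 | 19.7 |
| 50%, 6, 2.0, 4 | 69.5% | 65.6% | 46.2% | 3.9 | 23.3 |

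These rows include the extremes. Over all 24 scenarios, A − B runs from 0.0 to 5.4 points and A − C from 2.8 to 23.3.

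A second set of assumptions (35 against 65 children, ratio of days 1.7, 2,000 runs per setting) gives, for days against Yes-months:
- mean 3 days a month: 50 − 37 = 13 points;
- mean 8 days, high month-to-month variation: 51 − 34 = 17 points;
- mean 8 days, low variation: 55 − 28 = 27 points.

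Together, the loss under Yes-month scoring is about 3 to 27 points.

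**4. What the simulations leave out.** Neither set models the intermediate case, in which some entries can be coded and others cannot. If uncodable entries are commoner in children who use more, the codable remainder would also be selective. The gain from a numeric field is below A − C, because recalled days carry error too: in the third row it is 77.8 − 62.4 = 15.4 points if that error is as in B.

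**The case against.** The strongest objection is that the plan does collect amount. Question 5 asks for dose, frequency and duration whenever the answer is Yes, and section 6 promises dosage. A reader might infer that a child treated on 2 days and one treated on 25 days are recorded alike, so that amount of use is lost. The documents do not support that: it holds only if the completed blanks are discarded, and nothing in section 11 says they will be. This part of the objection stands. The defect is unreliable conversion, not absence of the information.

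A reader might also infer a definite power loss, such as 13 to 27 points. That does not hold either. It rests on assumed rates and on Yes-month scoring, and it falls to about 0 to 5 points when all the free text can be coded. Nor do the documents show that Yes-months will be frequent: they give no reliever-use rate, and children can enter from primary care records without a current attack.

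TRACK item 4 is a second, graded source, and its 3-month windows span the follow-up year. It can support the analysis. It does not replace a monthly amount: it is coarse, and TRACK is a separate secondary outcome.

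Finally, this is a feasibility study with no power claim for any outcome, so power is a weak yardstick. That is fair, and it limits the weight of the point. The need for usable pilot data remains.

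**Conclusion.** The point holds as a cheap improvement. Question 5 asks for the amount of rescue inhaler use in a form that cannot be reliably quantified when there are several episodes in a month or intermittent use, although the same questionnaire uses numeric days for two comparable outcomes. This follows from the documents alone.

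The statistical size does not. It depends on how much of the free text can be coded, with the range in the working as the conditional answer and no single figure defensible. The outcome is secondary, no conclusion of the study depends on it alone, and the severity is low.

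**What to change.** Add a numeric field to Question 5: *On how many days in the past month was the blue inhaler given?* (0 to 31). Keep the dose, frequency and duration blanks, so that the commitment to record dosage is still met and information on intensity within a day is not dropped.

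State in section 11 that the variable is total days of use divided by months with a returned questionnaire, compared between biomarker groups with the two-group test already planned there for quantitative variables.

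If the current form is already in use, write a rule for converting the three blanks to days before analysis, and report the share of entries that cannot be converted.

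The cost is one item on an electronic form and one or two sentences in the plan. The downside is that recalling days over a month is approximate, as it already is for Questions 2 and 6.
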